After midnight, the Investigator should optimize plasma glucose within a target range of 80 to 150 mg/dL (4.44 to 8.33 mmol/L) through the administration of IV/SC insulin and/or IV/oral glucose. If operational considerations at a site preclude IV administration of insulin overnight, no catheter will be placed, and oral glucose tablets and the subject's own insulin infusion pump will be used to optimize blood glucose within a target range of 80 to 150 mg/dL (4.44 to 8.33 mmol/L). This range is considered a target only, and values outside of this range will not be considered protocol deviations.

In the morning of the inpatient study visit, each subject's plasma glucose will be measured and verified to be within the range of 70 to 270 mg/dL (3.89 to 15.0 mmol/L) to confirm their eligibility for continuation to the insulin induction procedure. If this criterion is not met, the visit will be rescheduled after a minimum 3 day wait.

Subjects will continue to fast during the morning of the procedure and another IV catheter for blood sampling will be inserted in their contralateral arm. Ideally, the sampling IV catheter should be placed in a vein within the antecubital fossa. The hand used for blood sampling will be kept warm by use of a heated-hand box to increase blood flow to achieve "arterialized"

samples. The subject will be kept supine and the abdomen and torso will be covered under a blanket to maintain warmth.

The baseline euglycemic steady state period will begin when the plasma glucose is confirmed to be within the range of 70 to 270 mg/dL (3.89 to 15.0 mmol/L). IV insulin will be administered to maintain the plasma glucose concentration within the range of 75 to 115 mg/dL (4.17 to 6.83 mmol/L) for 30 minutes. If the plasma glucose has been maintained within the range of 75 to 115 mg/dL (4.17 to 6.83 mmol/L) for at least 30 minutes and the insulin infusion rate varies no more than $\pm 20\%$, the induction procedure may commence.

During the induction procedure, the subject will enter a state of hypoglycemia through the administration of regular insulin diluted in normal saline (see Section 7.2), within a controlled and monitored setting. Use of the insulin dose adjustment algorithm will be facilitated by real time data capture, allowing Sponsor personnel to monitor the induction procedures virtually in real time.

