7.2. Hypoglycemia Induction Procedure and Justification

The most commonly used hypoglycemia insulin induction method cited in the literature [Nerموen] involves constant insulin infusion rates many-fold above normal basal infusion rates. As hepatic glucose production is determined by the glucagon to insulin ratio, this procedure may not create realistic circumstances for evaluating the effectiveness of glucagon in raising blood glucose. A predecessor study (XSGP-301), therefore, utilized a comparatively lower rate of insulin infusion at 1 to 2 times the normal basal rate, combined with push of an IV bolus dose of insulin derived from the subject's own self-reported glucose correction factor. About 30% of the procedures performed in Study XSGP-301 resulted in plasma glucose < 40 mg/dL (< 2.22 mmol/L). To get more precision in achieving a steady state of plasma glucose below 50 mg/dL (2.78 mmol/L), individual procedure data from the Study XSGP-301 were fitted to a model of insulin action allowing identification of opportunities for algorithm enhancements. The algorithm was modified accordingly and tested in the model of the procedures representing a broad spectrum of subjects, including the two extremes of insulin sensitivity that were associated with low plasma glucose in Study XSGP-303. The algorithm was further refined for use in the current study based on experiences in the XSGP-303 trial.

Hypoglycemia Induction Procedure

The evening before treatments subjects will be admitted to the CRC and follow the procedures described in Table 5.

Baseline Euglycemic Steady State

Prior to starting the hypoglycemia induction procedure, the subject must have stable plasma glucose for at least 30 minutes at 95 ± 20 mg/dL (75 to 115 mg/dL [4.17 to 6.38 mmol/L]) and a stable IV insulin infusion rate varying no more than $\pm 20\%$ during which plasma glucose must be measured at least every 15 ± 2 minutes.

Induction Start

For the induction, the starting plasma glucose level will be determined as the average of the last three YSI measurements taken during the baseline steady state period (i.e., start of baseline, next after 15 minutes, end of baseline after 30-minute baseline confirmation period). The following procedures will then be performed:

1. Subjects will continue the IV insulin infusion at the final rate of the baseline euglycemic steady state.
2. Subjects then will be given an initial IV bolus push dose of regular insulin diluted in saline:

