 - a. The dose will be calculated as 75% of the dose estimated to reduce plasma glucose from the subject's starting plasma glucose level to 54 mg/dL (3 mmol/L) based on the subject's self-reported glucose correction factor. This dose will be referred to as "1 bolus (i.e., full bolus dose)" subsequently. The Investigator may use discretion to decrease the amount of the calculated bolus dose based upon the subject's insulin sensitivity factor. However, the Investigator is not allowed to increase the amount of the bolus dose.
 - b. Plasma glucose will be measured every 5 to 10 minutes, depending on the current plasma glucose value (see [Table 4](#)).
 - c. The first insulin adjustment will be made no earlier than 20 minutes after the initial bolus but will otherwise follow the directions for insulin adjustments shown in [Table 4](#).

The Investigator may override the insulin dosing algorithm at their discretion. Note: investigator does not have discretion to give bolus doses once plasma glucose is 65 mg/dL (3.3 mmol/L) or less (see numbers 3.b.i and 4.b.i below).

When plasma glucose is > 80 mg/dL (> 4.44 mmol/L), insulin adjustments should not be made more frequently than every 10 minutes. When plasma glucose is ≤ 80 mg/dL (≤ 4.44 mmol/L), the minimum time between adjustments to decrease, terminate or re-start insulin is either 10 or 5 minutes, as indicated in [Table 4](#).

1. While plasma glucose is > 80 mg/dL (> 4.4 mM/L):
 - a. Measure plasma glucose every 10 minutes.
 - b. When 10 minutes have passed from the last insulin dose adjustment:
 - i. Bolus: If the rate of plasma glucose decrease is < 0.15 mg/dL·min (< 0.01 mM/min), then an additional 1 bolus (full bolus dose) should be administered.

- ii. Infusion Rate: If the rate of plasma glucose decrease is $< 0.5 \text{ mg/dL}\cdot\text{min}$ ($< 0.03 \text{ mM/min}$), then the insulin infusion rate should be increased by 20%.
 2. While plasma glucose is 66 to 80 mg/dL (3.66-4.4 mM/L):
 - a. Measure plasma glucose every 5 minutes.
 - b. When 10 minutes have passed from the last insulin dose adjustment:
 - i. Bolus: If the rate of plasma glucose decrease is $< 0.15 \text{ mg/dL}\cdot\text{min}$ ($< 0.01 \text{ mM/min}$), then an additional 1/2 bolus (half-bolus dose) should be administered.
 - ii. Infusion Rate:
 - 1) If the rate of plasma glucose decrease is $< 0.33 \text{ mg/dL}\cdot\text{min}$ ($< 0.02 \text{ mM/min}$), then the insulin infusion rate should be increased by 20%.

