At any time, the induction procedure may be terminated at the Investigator's discretion. If the procedure is terminated, appropriate measures (oral or IV glucose) will be administered at the Investigator's discretion. If a subject exhibits signs of coma or convulsions, a IV bolus dose of dextrose will be given per standard of practice. Signs and symptoms should be monitored, and if the subject's condition fails to improve in a timely manner, additional dextrose or other medical interventions may be given at the Investigator's discretion.

Note: Study glucagon should NOT be administered as hypoglycemia rescue in this context.

Euglycemia will be confirmed and the subject should be medically stabilized per Investigator discretion before being released. The treatment visits should be rescheduled after a minimum 3-day wait.

If an SAE occurs during hypoglycemia induction, the procedure will end, and IV insulin will be safely withdrawn. Causality should be fully assessed by both the Investigator and the Sponsor.

Note: subjects will undergo a maximum of 4 hypoglycemia inductions in this study to achieve two successful procedures.

Table 4 Insulin Dose Adjustments

Plasma Glucose		Measurement Interval (minutes)	Target Rate of Plasma Glucose Decrease	Insulin Bolus Criteria	Insulin Basal Rate Adjustment Criteria
(mg/dL)	(mmol/L)				
> 80	> 4.44	10	> 0.5 mg/(dL·min) (> 0.03 mM/min)	If plasma glucose ↓ < 0.15 mg/(dL·min) (< 0.01 mM/min); give 1 bolus	If plasma glucose ↓ < 0.5 mg/dL·min (< 0.03 mM/min), ↑ 20% (10 min)
66-80	3.66-4.44	5	0.33-0.5 mg/(dL·min) (0.02-0.03 mM/min)	If plasma glucose ↓ < 0.15 mg/(dL·min) (< 0.01 mM/min); give ½ bolus	If plasma glucose ↓ < 0.33 mg/dL·min (< 0.02 mM/min), ↑ 20% (10 min)
					If plasma glucose ↓ > 0.5 mg/dL·min (> 0.03 mM/min), ↓ 20% (10 min)
61-65	3.39-3.61	5	0.25-0.33 mg/(dL·min) (0.014-0.02 mM/min)	Not allowed	If plasma glucose ↓ < 0.25 mg/dL·min (< 0.01 mM/min), ↑ 20% (10 min)
					If plasma glucose ↓ > 0.33 mg/dL·min (> 0.02 mM/min), ↓ 20% (10 min)
54-60	3-3.33	5	0.15-0.25 mg/(dL·min) (0.008-0.014 mM/min)	Not allowed	If plasma glucose ↓ < 0.15 mg/dL·min (< 0.008 mM/min), ↑ 20% (10 min); or If insulin infusion rate was previously set to baseline or the insulin infusion rate was ↓ by 50%, then set new insulin infusion rate at 120% of the prior rate (5 min) Note: This escalation in rate can be performed every 5 minutes until the rate of decrease is > 0.15 mg/dL·hr (> 0.008 mM/hr)

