8.3. Randomization

Subjects who meet all eligibility criteria, who reach the baseline euglycemia steady state, and who the Investigator deems appropriate to begin the induction procedure (see Section 10.2) at the first treatment visit will be randomized for the study. The randomization schedule will be produced by the Study statistician a priori for loading and implementing in the Interactive Web-based Randomization System (IWRS). Using a permuted random block assignment, stratified by site, subjects will be randomly assigned to receive either Treatment Sequence 1 (G-Pen → GlucaGen Hypokit) or Treatment Sequence 2 (GlucaGen Hypokit → G-Pen).

Once a subject has been randomized, information regarding the glucagon (G-Pen or GlucaGen Hypokit) to be administered to the subject at each of the treatment visits will be viewable by study staff in the Dose Administration form in the electronic data capture (EDC) system.

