9.3.3. Preparation, Dispensing and Administration

G-Pen will be supplied as 0.2 mL of non-aqueous solution in a plastic Crystal Zenith 1 mL long syringe loaded into a Molly disposable AI. Subcutaneous administration will be performed by a qualified CRC staff member who has read the written Instructions for Use provided by Xeris.

In the case of GlucaGen Hypokit, a new vial of lyophilized glucagon will be fully reconstituted immediately prior to abdominal administration using 1 mL of sterile diluent provided in the commercial kit as per the GlucaGen Hypokit Summary of Product Characteristics (SmPC) and Prescribing Instructions [[Novo Hypokit](#)].

Study drug will be administered according to the randomization schedule accessed in the EDC system (see 8.3). Randomization will occur at the start of the induction procedure, or about 2 to 3 hours prior to administration of study drug. When the Investigator believes the hypoglycemia induction procedure is approximately 1 hour from completion, a member of the study team will deliver the correct investigational product (IP) for the visit to the clinic area, making sure to maintain subject blinding.

The study drugs will not be prepared ahead of time. Instead, preparation of the investigational product (IP) (i.e., re-constitution of GlucaGen Hypokit) will begin *after* the confirmatory plasma glucose reading is obtained, indicating that a hypoglycemic steady state has been achieved, i.e., upon a “decision to dose.”

G-Pen is being developed for SC injection. The marketed comparator is labeled for both SC and intramuscular (IM) injection. Both products will be administered via the SC route to the abdomen, around the umbilicus.

The G-Pen auto-injector is made to be pressed against the skin perpendicularly (i.e., at a 90° angle) to the injection site. The injection technique for G-Pen will follow printed instructions for use (IFU) provided by Xeris.

For GlucaGen Hypokit, the skin should be pinched to avoid an IM injection. The needle will be inserted into the loose tissue under the injection site at a 90° angle and the product injected smoothly over 1 to 3 seconds. Following injection, light pressure should be applied to the injection site, as the needle is withdrawn.

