1. Subjects will continue the IV insulin infusion at the final rate of the euglycemic steady state.
2. Subjects will be given an initial IV bolus push dose of regular insulin diluted in saline:
 - a. The dose will be calculated as 75% of the dose estimated to reduce plasma glucose from the subject's starting plasma glucose level to 54 mg/dL (3.0 mmol/L) based on the subject's self-reported glucose correction factor. This dose will be referred to as "1 bolus (full bolus dose)" subsequently.
 - b. Plasma glucose will be measured no less frequently than every 10 minutes.

The first insulin adjustment will be no earlier than 20 minutes after the initial bolus but will otherwise follow the directions for insulin adjustments shown in Section 7.2 (see also Table 4).

Insulin Dose Adjustments

Insulin dose adjustments will be performed as outlined in Section 7.2 (see also Table 4).

Randomization

Once the initial bolus dose of insulin has had time to take effect and the subjects is observed to be in a controlled rate of glucose decline, which will generally occur at approximately 30 to 60 minutes after the beginning of the induction period, the subject will be randomly assigned to receive either G-Pen or GlucaGen Hypokit in one of the treatment sequences shown in Table 3.

Confirmation of Hypoglycemic Steady State

Once the initial plasma glucose measurement < 54.0 mg/dL (< 3 mmol/L) is achieved, the IV insulin infusion will be returned to the rate established at the end of the baseline euglycemia steady state period. After 5 minutes, the IV insulin infusion will be stopped, and up to 3 confirmatory plasma glucose readings will be taken at subsequent 5-minute intervals to determine whether a hypoglycemic steady state has been reached.

A hypoglycemic steady state is defined as a confirmatory plasma glucose value ≥ 42 mg/dL (≥ 2.33 mmol/L) and < 54 mg/dL (< 3 mmol/L), and an 8-minute linearly extrapolated future plasma glucose value ≥ 42 mg/dL (≥ 2.33 mmol/L).

To determine whether a hypoglycemic steady state has been achieved, confirmatory plasma glucose measurements will be taken as necessary at 5, 10 and 15 minutes after an initial plasma glucose < 54 mg/dL (< 3 mmol/L). Depending on the outcome, the following procedures will be followed.

1. If any of the confirmatory measurements meets the criteria for hypoglycemic steady state, the subject will be eligible to receive study glucagon, and further confirmatory plasma glucose measurement are not required.

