2. If the final confirmatory plasma glucose value is < 42 mg/dL (< 2.33 mmol/L), the procedure will be terminated, study glucagon will NOT be administered, and the visit will be rescheduled after a minimum 3-day wait. At the Investigator's discretion, the subject should be treated with IV glucose or oral carbohydrates, it should be verified that the subject achieved a euglycemic state and is medially stable prior to discharge.
3. If any of the confirmatory plasma glucose measurements are > 54 mg/dL (> 3 mmol/L), then the IV insulin infusion will be re-started, and insulin adjustments will be made as per the induction procedure described above (see [Table 4](#)). Once another initial plasma < 54 mg/dL (< 3 mmol/L) is obtained, the sequence of up to 3 confirmatory plasma glucose readings will be repeated.

Note: If a subject fails to achieve a hypoglycemic steady state within 60 minutes of the first plasma glucose measurement < 54 mg/dL (< 3 mmol/L), the procedure will be terminated, and the visit re-scheduled after a minimum 3-day wait.

Decision to Dose

If the subject is deemed to be within a hypoglycemic steady state, then the subject is ready to be dosed with study drug (decision to dose). At this time, the subject will be eligible to receive the randomized study drug.

Preparation and Administration of Study Drug

1. Once the induction procedure has begun and glucose < 54 mg/dL (< 3 mmol/L) is predicted to occur within approximately 1 hour, the study staff member who will be performing the study drug injection should be notified that the induction procedure is reaching conclusion. At this time the study staff member will bring the appropriate unopened test article (pouched G-Pen or Novo GlucaGen Hypokit kit) to the bedside, as assigned by the EDC system.
2. Once the hypoglycemic steady state is confirmed, the Investigator will confirm that it is appropriate to administer study drug to the subject. The clock time of this "Decision to Dose" will be captured in the source documents.
3. At this point, the subject will receive the blindfold and headphones with music playing to maintain the blind.
4. The treatment administrator will then open the study drug container (kit or pouch) and begin preparation of the glucagon for administration following the applicable IFU. An Investigator should verify that the contents of the vial of lyophilized GlucaGen Hypokit have been fully reconstituted prior to administration.

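### The assigned drug for both visits is visible to study staff before the decision to dose, while those running the induction keep bounded discretion over insulin, termination and dosing; the display should be delayed

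*Protocol*

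**What the plan says.** **Who sees the allocation.** Under Protocol 8.3, information on the glucagon "to be administered to the subject at each of the treatment visits will be viewable by study staff in the Dose Administration form" once the subject is randomized. Protocol 9.2 blinds the subject only, and SAP 4.4 says the investigator and clinical staff know the treatment.

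**When.** Protocol 9.3.3 states: "Randomization will occur at the start of the induction procedure, or about 2 to 3 hours prior to administration of study drug". Protocol 10.2.1.2 places randomization later, once glucose is falling in a controlled way, "which will generally occur at approximately 30 to 60 minutes after the beginning of the induction period". On either timing it comes before the decision to dose. Visit 3 follows 7 to 28 days after the first treatment visit (Protocol 10.2.2), so the second drug is already on display at admission.

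**What the investigator may decide meanwhile.**
- Protocol 7.2: "The Investigator may override the insulin dosing algorithm at their discretion". The calculated bolus may also be reduced.
- Protocol 7.2: "At any time, the induction procedure may be terminated at the" investigator's discretion. The visit is then rescheduled, with at most four inductions per subject to obtain two successful ones.
- Protocol 10.2.1.2: after steady state is confirmed, "the Investigator will confirm that it is appropriate to administer study drug to the subject".

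**Who else watches.** Protocol 7.1 describes real-time data capture "allowing Sponsor personnel to monitor the induction procedures virtually in real time". It does not say whether those personnel can see the allocation.

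**The concern.** The two devices differ, so whoever injects must know the product. The documents give no reason why the person adjusting insulin should know it hours earlier. No section withholds the drug from that person until the decision to dose.

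This bears on the endpoint. In justifying its induction method, Protocol 7.2 reasons: "As hepatic glucose production is determined by the glucagon to insulin ratio". Insulin exposure before the injection is therefore part of the condition under which each drug is tested. If overrides, terminations or dosing confirmations leaned toward or against one drug, its failure rate could move for reasons unrelated to the drug. The crossover removes differences between subjects. It does not remove a lean that follows the drug. Success is expected to be close to 100% (Protocol 13.2), so few failures will decide the comparison.

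**Working it through.** The plan gives no figure on this point to reproduce. The check sets the rules side by side, then asks how many outcomes separate passing from failing.

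**1. Knowledge against discretion**

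| Stage | Drug visible? | Open discretion | Fixed limits |
|---|---|---|---|
| Period 1, baseline and first bolus | Yes if randomized at the start of induction (9.3.3); no if 30 to 60 minutes in (10.2.1.2) | Reduce the bolus | Bolus may not be increased (7.2) |
| Period 1, rest of induction | Yes on both timings | Override, terminate and repeat | No bolus at 65 mg/dL or below (7.2) |
| Period 1, confirmation and dosing | Yes | Confirm that dosing is appropriate | See the list below |
| Period 1 visit rescheduled after randomization | Yes, throughout | All of the above | All of the above and below |
| Period 2 | Yes, from before admission | All of the above | All of the above and below |

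The limits at confirmation and dosing are these:
- After the first reading below 54 mg/dL, insulin returns to the baseline rate for 5 minutes and then stops (7.1, 7.2, 10.2.1.2).
- Eligibility needs a confirmatory value of at least 42 and below 54 mg/dL, with an 8-minute extrapolation of at least 42. It is met at the first qualifying reading (10.2.1.2).
- Steady state must be reached within 60 minutes of the first reading below 54 (10.2.1.2).
- Dosing outside steady state is a major violation (7.3).

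These rules fix the final insulin step and the glucose window. They do not fix earlier boluses and rate changes, or whether an induction is abandoned and repeated. SAP 6.5 counts a missing outcome as a failure, but an induction that is ended and later repeated successfully is not missing.

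**2. What the SAP would show**

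It plans a mean glucose curve during induction by treatment (6.6.2), an induction listing (Listing 16.2.5.2), and individual glucose and insulin induction profiles by treatment (Figure 14.2.4.1). It plans no tabulation by drug of overrides, terminated or repeated inductions, insulin exposure, or glucose at dosing.

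**3. How few outcomes decide the verdict**

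Inputs: 122 randomized (SAP 4.2); upper 95% limit of the failure-rate difference at most 5%, with a G-Pen failure rate at most 5% (SAP 6.5); unpaired risk difference (SAP Appendix 2, PROC FREQ with riskdiff, Wald by default).

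With k G-Pen failures, no GlucaGen failures and p = k/n, the upper limit is p + 1.96 × √(p(1 − p)/n).

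- n = 122, k = 2: 1.64% + 1.96 × 1.150% = **3.89%**, pass.
- n = 122, k = 3: 2.46% + 1.96 × 1.402% = **5.21%**, fail.
- n = 111 (the evaluable goal): 4.28% at k = 2 (pass) and 5.72% at k = 3 (fail).

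With r GlucaGen failures, the term under the root adds the same expression for r/n, and r/n is subtracted from p. At n = 122 and r = 1, three G-Pen failures give 4.82% (pass) and four give 6.00% (fail). At r = 3, three give 3.89% (pass) and four give 5.01% (fail).

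In each case one further G-Pen failure reverses the conclusion.

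**The case against.** The strongest reply is that this is a declared single-blind design, stated in Protocol 9.2 and SAP 4.4, with an analyzer-measured endpoint and a tightly scripted induction. The limits listed above leave little room, sponsor monitoring is described as support for the algorithm, and part of the induction data is already shown by treatment. Sensitivity to a single outcome comes from the margin and the sample size; it is not evidence of bias.

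Most of this stands. The limits are real, the measurement is objective, and the single-outcome sensitivity would exist under perfect concealment. It does not answer the narrower question. Subject-only blinding explains open injection, but it gives no reason to show the drug during induction, and Protocol 10.2.1.2 already has a staff member who fetches and injects the product.

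A reader might infer that inductions will be steered, or try to put a size on it. For example, one could assume a normal 30-minute rise with SD 15 to 30 mg/dL, a true failure rate of 5% against 0%, and G-Pen inductions easier by 2 to 4 mg/dL. False non-inferiority would then rise from about 5% to between 10% and 33%. The documents support none of those inputs.

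The dosing window alone would not yield such shifts. Under SAP 5.3.6.1 the rise needed is min(20, 70 − baseline): 20 mg/dL at 50 or below and 16.1 at 53.9. Suppose every G-Pen dose fell uniformly between 50 and 53.9 and every GlucaGen dose uniformly between 42 and 53.9. The mean bar would be 70 − 51.95 = 18.05 against 20 − (3.9/11.9) × 1.95 = 19.36, a difference of 1.3 mg/dL. Even that is an extreme imbalance.

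**Conclusion.** The point holds as an avoidable weakness in concealment. Allocation is visible before the decision to dose on either stated randomization time, and before admission in period 2, to a group that may include those with discretion over the induction. That discretion is bounded. No lean is shown, it may be zero, and its size cannot be derived from the documents. The case for acting is that the route serves no stated purpose, a difference of one outcome can change the verdict (3.89% against 5.21%), and closing most of it costs little.

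The two limits assume the unpaired Wald interval, 122 outcomes per drug and no GlucaGen failures, including none imputed for missing data. They show how sensitive the verdict is. They do not estimate bias.

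**What to change.** **Protocol 8.3 and 9.3.3.** Show the assigned drug only to the staff member who fetches and injects the product. Hide it from the investigator running the induction, and from sponsor personnel following it, until that visit's decision-to-dose time has been entered in the EDC.

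**Protocol 10.2.1.2, preparation step 1.** Keep the unopened product in an opaque bag until then.

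**Protocol 9.2 and SAP 4.4.** Align the wording, so that the investigator is described as aware of treatment only from the decision to dose.

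**SAP.** Add to the planned induction outputs one descriptive table by assigned drug: glucose at dosing, insulin rate and exposure before dosing, algorithm overrides, and terminated or repeated inductions.

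**State the limit openly.** Period 2 concealment is only partial, because anyone who saw the period 1 injection can infer the second drug. A different investigator should not be required for period 2: it burdens staffing and works against the aim in Protocol 10.2.1.2 that the same investigator assess injection sites at both visits. The table is therefore the main safeguard for period 2.

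**Cost.** An EDC viewing permission, a few sentences, an opaque bag and one table. The small downside is that the injector must not disclose the drug before the decision to dose. No insulin or dosing rule changes.
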